8.4.4. Medically Attended Adverse Events

An MAAE is an AE that leads to an unscheduled visit to an HCP. This would include visits to a study site for unscheduled assessments (eg, abnormal laboratory follow-up, and/or COVID-19

[[Section 8.1.6](#)]) and visits to HCPs external to the study site (eg, urgent care, primary care physician). Investigators will review unsolicited AEs for the occurrence of any MAAEs. Unsolicited AEs will be recorded in the AE section of the eCRF.

All cases of RT-PCR-confirmed ILI and/or confirmed COVID-19 will be recorded as MAAEs.

8.4.5. Anaphylaxis

All suspected cases of anaphylaxis should be recorded as MAAEs and reported as an SAE, based on the criteria for a medically important event, unless the event meets other serious criteria. As an SAE, the event should be reported to the Sponsor or designee immediately and in all circumstances within 24 hours, per [Section 8.4.13](#). The Investigator will submit any updated anaphylaxis case data to the Sponsor within 24 hours of it being available. For reporting purposes, a participant who displays signs or symptoms consistent with anaphylaxis (as described below) should be reported as a potential case of anaphylaxis. This is provided as general guidance for Investigators and is based on the Brighton Collaboration case definition ([Rüggeberg et al 2007](#)).

Anaphylaxis is an acute hypersensitivity reaction with multi-organ system involvement that can present as, or rapidly progress to, a severe life-threatening reaction. It may occur following exposure to allergens from a variety of sources.

Anaphylaxis is a clinical syndrome characterized by the following:

- Sudden onset AND
- Rapid progression of signs and symptoms AND
- Involves 2 or more organ systems, as follows:
 - **Skin/mucosal:** urticaria (hives), generalized erythema, angioedema, generalized pruritus with skin rash, generalized prickle sensation, red and itchy eyes.
 - **Cardiovascular:** measured hypotension, clinical diagnosis of uncompensated shock, loss of consciousness or decreased level of consciousness, evidence of reduced peripheral circulation.
 - **Respiratory:** bilateral wheeze (bronchospasm), difficulty breathing, stridor, upper airway swelling (lip, tongue, throat, uvula, or larynx), respiratory distress, persistent dry cough, hoarse voice, sensation of throat closure, sneezing, rhinorrhea.
 - **Gastrointestinal:** diarrhea, abdominal pain, nausea, vomiting.

8.4.6. Influenza-Like Illness

A protocol-defined ILI is determined by the occurrence of at least 1 respiratory illness symptom concurrently with at least 1 systemic symptom, or the occurrence of any 2 or more respiratory symptoms.

Respiratory Symptoms	Systemic Symptoms

1. Sore throat2. Cough/rhinorrhea/nasal congestion (\geq 1 of the 3 symptoms count as 1 respiratory symptom)3. Sputum production4. Wheezing5. Difficulty breathing	
1. Body temperature $> 37.2^{\circ}\text{C}$ ($> 99^{\circ}\text{F}$)2. Chills3. Tiredness4. Headache5. Myalgia6. Nausea/Vomiting7. Diarrhea

A CDC-defined ILI is defined as body temperature $\geq 37.8^{\circ}\text{C}$ (100°F) accompanied by cough and/or sore throat.

An RT-PCR-confirmed ILI is defined as a positive influenza result by RT-PCR done at any setting during the study period.

8.4.7. Adverse Events of Special Interest

An AESI is an AE (serious or nonserious) of scientific and medical concern specific to the Sponsor's product or program, for which ongoing monitoring and immediate notification by the Investigator to the Sponsor are required. Such events may require further investigation to characterize and understand them.

Adverse events of special interest for this protocol are listed in Appendix 3 ([Section 11.3](#)).

All AESIs will be collected through the entire study period and must be reported to the Sponsor or designee immediately and in all circumstances within 24 hours of becoming aware of the event via the electronic data capture (EDC) system. If a site receives a report of a new AESI from a participant or receives updated information on a previously reported AESI at a time after the eCRF has been taken offline, then the site can report this information on a paper AESI form using the SAE Mailbox.

Myocarditis/Pericarditis

A case of suspected, probable, or confirmed myocarditis, pericarditis, or myopericarditis should be reported as an AESI, even if it does not meet criteria per the CDC case definition. The event

should also be reported as an SAE if it meets seriousness criteria ([Section 8.4.2](#)). The CDC case definition is provided in [Section 11.4](#) as guidance.

8.4.8. Recording and Follow-Up of Pregnancy

Female participants who have a positive pregnancy test at screening should not be enrolled; participants who have a positive pregnancy test at Day 1 should not receive the IP.

Details of all pregnancies in female participants will be collected after the study vaccination on Day 1 and until the end of their participation in the study. If a pregnancy is reported, the Investigator should inform the Sponsor within 24 hours of learning of the pregnancy and should follow the procedures outlined in this section. Abnormal pregnancy outcomes (eg, spontaneous abortion, fetal death, stillbirth, congenital anomalies, ectopic pregnancy) are considered SAEs.

Pregnancies occurring in participants after enrollment must be reported to Sponsor or designee within 24 hours of the site learning of its occurrence, using the SAE Mailbox, the SAE Hotline, or the SAE Fax line ([Section 8.4.13](#)). If the participant agrees to submit this information, the pregnancy must be followed to determine the outcome, including spontaneous or voluntary termination, details of the birth, and the presence or absence of any birth defects, congenital abnormalities, or maternal and/or newborn complications. This follow-up should occur even if intended duration of the safety follow-up for the study has ended. Pregnancy report forms will be distributed to the study site to be used for this purpose. The Investigator must immediately (within 24 hours of awareness) report to the Sponsor any pregnancy resulting in an abnormal outcome according to the procedures described for SAEs.

8.4.9. Eliciting and Documenting Adverse Events

The Investigator is responsible for ensuring that all AEs and SAEs are recorded in the eCRF and reported to the Sponsor.

Solicited ARs will be collected from Day 1 through 7 days after the vaccine dose. Other (unsolicited) AEs will be collected from Day 1 through 28 days after the vaccine dose.

The MAAEs, SAEs, and AESIs will be collected from participants as specified in the SoE ([Table 1](#), [Table 2](#), and [Table 3](#)) until the end of their participation in the study. Any AEs occurring before receipt of the IP will be analyzed separately from AEs.

At every study site visit or telephone contact, participants will be asked a standard question to elicit any medically related changes in their well-being (including respiratory viral infection symptoms) according to the scripts provided. Participants will also be asked if they have been hospitalized, had any accidents, used any new medications, changed concomitant medication regimens (both prescription and over-the-counter medications), or had any nonstudy vaccinations.

In addition to participant observations, physical examination findings and other documents relevant to participant safety classified as an AE will be documented in the AE section of the eCRF.

After the initial AE/SAE report, the Investigator is required to proactively follow each participant at subsequent visits/contacts. All AEs and SAEs will be treated as medically appropriate and followed until resolution, stabilization, the event is otherwise explained, or the participant is LTFU (as defined in [Section 7.4](#)).

8.4.10. Assessment of Intensity

An event is defined as “serious” when it meets at least 1 of the predefined outcomes as described in the definition of an SAE ([Section 8.4.2](#)), NOT when it is rated as severe.

The severity (or intensity) of an AR or AE refers to the extent to which it affects the participant’s daily activities. The toxicity grading scale for healthy adult and adolescent volunteers enrolled in preventive vaccine clinical trials ([DHHS 2007b](#)) will be used to categorize local and systemic reactogenicity events (solicited ARs), clinical laboratory test results, and vital sign measurements observed during this study. Specific criteria for local and systemic reactogenicity events are presented in [Section 8.4.3](#).

The determination of severity for all unsolicited AEs should be made by the Investigator based upon medical judgment and the definitions of severity as follows:

- Mild: These events do not interfere with the participant’s daily activities.
- Moderate: These events cause some interference with the participant’s daily activities and require limited or no medical intervention.
- Severe: These events prevent the participant’s daily activity and require intensive therapeutic intervention.

Study staff should elicit from the participant the impact of AEs on the participant’s activities of daily living to assess severity and document appropriately in the participant’s source documentation. Changes in the severity of an AE should be documented in the participant’s source documentation to allow an assessment of the duration of the event at each level of intensity to be performed. An AE characterized as intermittent requires documentation of onset and duration of each episode. An AE that fluctuates in severity during the course of the event is reported once in the eCRF at the highest severity observed.

8.4.11. Assessment of Causality

The Investigator’s assessment of an AE’s relationship to the IP is part of the documentation process but is not a factor in determining what is or is not reported in the study.

The Investigator will assess causality (ie, whether there is a reasonable possibility that the IP caused the event) for all AEs and SAEs. The relationship will be characterized using the following classification:

- **Not related:** There is not a reasonable possibility of a relationship to the IP. Participant did not receive the IP OR the temporal sequence of AE onset relative to administration of the IP is not reasonable OR the AE is more likely explained by another cause than the IP.
- **Related:** There is a reasonable possibility of a relationship to the IP. There is evidence of exposure to the IP. The temporal sequence of the AE onset relative to the administration of the IP is reasonable. The AE is more likely explained by the IP than by another cause.

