8.4. Safety Definitions and Related Procedures

8.4.1. Adverse Event

An AE is defined as any untoward medical occurrence associated with the use of a drug/vaccine in humans, whether or not considered related to the drug/vaccine.

Events Meeting the Adverse Event Definition

- Exacerbation of a chronic or intermittent pre-existing condition, including an increase in frequency and/or intensity of the condition, after the IP injection.
- New conditions detected or diagnosed after the IP injection even though they may have been present before the start of the study.

Events NOT Meeting the Adverse Event Definition

- Procedures planned before study entry (eg, hospitalization for preplanned surgical procedure).
- Medical or surgical procedure (eg, endoscopy, appendectomy): the condition that leads to the procedure should be the AE.
- Situations in which an untoward medical occurrence did not occur (social and/or convenience admission to a hospital).

An AR is any AE for which there is a reasonable possibility that the vaccine caused the AE ([Section 8.4.3](#)). For the purposes of IND safety reporting, “reasonable possibility” means that there is evidence to suggest a causal relationship between the vaccine and the AE.

An unsolicited AE is any AE reported by the participant that is not specified as a solicited AR in the protocol or is specified as a solicited AR but starts outside the protocol-defined period for reporting solicited ARs (ie, 7 days after vaccine administration).

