8.4.13. Reporting Serious Adverse Events

Prompt notification by the Investigator to the Sponsor of an SAE is essential so that legal obligations and ethical responsibilities toward the safety of participants and the safety of a study intervention under clinical investigation are met.

Any AE considered serious by the Investigator or that meets SAE criteria ([Section 8.4.2](#)) must be reported to the Sponsor immediately (within 24 hours of becoming aware of the SAE) via the EDC

system. The Investigator will assess whether there is a reasonable possibility that the IP caused the SAE. The Sponsor will be responsible for notifying the relevant regulatory authorities of any SAE as outlined in 21 US CFR Parts 312 and 320. The Investigator is responsible for notifying the institutional review board (IRB) directly.

If the eCRF is unavailable at the time of the SAE, the following contact information is to be used for SAE reporting:

- SAE Mailbox: PPD [REDACTED]
- SAE Hotline (USA): PPD [REDACTED]
- SAE Fax Line (USA): PPD [REDACTED]

Regulatory reporting requirements for SAEs are described in [Section 8.4.18](#).

The Investigator and any qualified designees are responsible for detecting, documenting, and recording events that meet the definition of an AE, including SAEs, and remain responsible for following up AEs that are serious, considered related to the IP or study procedures, or that caused the participant to discontinue the study.

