6.3.1.2 TEAEs by System Organ Class and Preferred Term

The following summary tables of TEAEs will be provided by SOC and PT using frequency counts and percentages (i.e., number and percentage of participants with an event):

- All unsolicited TEAEs
- All unsolicited TEAEs that are treatment-related
- All unsolicited serious TEAEs
- All unsolicited serious TEAEs that are treatment-related
- All unsolicited TEAEs leading to discontinuation from participation in the study
- All unsolicited severe TEAEs
- All unsolicited severe TEAEs that are treatment-related
- All unsolicited treatment-emergent AESI

- All unsolicited medically attended TEAEs
- All unsolicited medically attended TEAEs that are treatment-related

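### Protocol 8.4.11 sets reasonable possibility as the causality test, yet lets a likelier alternative cause alone make an AE not related

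*Protocol*

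**What the plan says.** Protocol section 8.4.11 opens with the standard: "The Investigator will assess causality (ie, whether there is a reasonable possibility that the IP caused the event) for all AEs and SAEs". It then gives two categories.

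- *Related* begins "There is a reasonable possibility of a relationship to the IP". It goes on to exposure and timing, and ends with "The AE is more likely explained by the IP than by another cause".
- *Not related* begins with the negation of that first sentence and lists three grounds joined by OR: the IP was not received, the timing is not reasonable, or "the AE is more likely explained by another cause than the IP".

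The other statements of the standard contain no comparison between causes. Section 8.4.1 says "An AR is any AE for which there is a reasonable possibility that the vaccine caused the AE" and adds that, for IND safety reporting, reasonable possibility "means that there is evidence to suggest a causal relationship between the vaccine and the AE". Section 8.4.13 says of SAEs: "The Investigator will assess whether there is a reasonable possibility that the IP caused the SAE". SAP section 6.3.2 defines an AR in the same way.

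The classification is used in the treatment-related rows of protocol Table 15, in the treatment-related counterpart of each category in SAP section 6.3.1.1, in the SAP section 6.3.1.2 tables such as "All unsolicited TEAEs that are treatment-related" (also serious, severe and medically attended), and in the severity tables of SAP section 6.3.1.3.

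**The concern.** Reasonable possibility and likelier-than-any-other-cause are different thresholds. An event can have a genuine possibility of being due to the vaccine while something else is the better explanation. Section 8.4.11 places such an event in a category whose opening sentence denies any reasonable possibility, so the section contradicts its own lead sentence.

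Competing explanations are foreseeable here. COVID-19 vaccines are exempt from the 28-day vaccine exclusion, and section 8.1.6 expects intercurrent SARS-CoV-2 infection and influenza-like illness. At stake is what the treatment-related tables mean. Depending on which sentence an investigator follows, the same event may or may not appear in them.

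**Working it through.** No figure in the plan depends on this definition, so the check is mainly one of logic.

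**Step 1: sort AEs by type.** The middle column applies the stated standard (8.4.11 lead sentence, 8.4.1, 8.4.13, SAP 6.3.2). The right column applies the full 8.4.11 category text.

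| Type of unsolicited AE | Reasonable possibility alone | 8.4.11 as written |
|---|---|---|
| A: no reasonable possibility | Not related | Not related |
| B: reasonable possibility, vaccine likelier | Related | Related |
| C: reasonable possibility, other cause likelier | Related | Not related (one OR ground is enough) |
| D: reasonable possibility, equally likely | Related | Unclear: fails the comparison in *Related*, but also misses the comparative ground in *Not related* |

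**Step 2: direction.** Let B, C and D be the numbers of such events.

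- Related under the stated standard = B + C + D.
- Related as written = B, or B + D if ties are accepted.

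The second cannot exceed the first. The same holds for participants, although a participant leaves the related count only if none of their AEs remains classed as related.

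**Step 3: size.** The reduction depends on the share f of reasonable-possibility AEs that the comparison moves out. The documents do not give f, so no size follows from them.

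**Step 4: illustration only.** Protocol section 9.3 gives the chance of seeing at least one participant with an AE, which is 1 − (1 − p)^n. This reproduces:

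- n = 45: 90.1% at 5% and 99.1% at 10% (stated: about 90% and 99%).
- n = 150: 95.2% at 2% and 99.0% at 3% (stated: at least 95%, and 99%).
- n = 50: 92.3% at 5% and 99.5% at 10% (stated: about 92% and 99%).

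Now assume that p is the incidence of AEs meeting the reasonable-possibility standard, with one such AE per affected participant. Replace p by p(1 − f). The expected number classed related is n·p·(1 − f), and the chance of at least one is 1 − (1 − p(1 − f))^n.

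| Assumed f | n = 150, p = 2%: expected | At least one | n = 50, p = 5%: expected | At least one |
|---|---|---|---|---|
| 0 | 3.00 | 95.2% | 2.50 | 92.3% |
| 0.25 | 2.25 | 89.6% | 1.88 | 85.2% |
| 0.50 | 1.50 | 77.9% | 1.25 | 71.8% |
| 0.75 | 0.75 | 52.9% | 0.62 | 46.7% |

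The table shows how the count would respond to f. It is not an estimate of f. Section 9.3 speaks of AEs in general, not related AEs, so the plan's own figures are not in question.

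**The case against.** The lead sentence can be read as governing. It tells the investigator to judge reasonable possibility, and both categories open with that test, so the comparative clauses may be taken as guidance. An investigator who reads it that way loses nothing. This stands, and it makes any under-count conditional. It does not remove the contradiction, because the OR list makes a likelier alternative sufficient by itself.

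A reader might infer several stronger things that the documents do not support.

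- *That suspected-reaction reporting under the IND rests on this classification.* Section 8.4.13 applies the plain standard to SAEs, with no comparison. All SAEs go to the sponsor within 24 hours, and AESIs do so whatever their relationship. Section 8.4.11 itself says causality does not decide what is reported. For SAEs learned of after a participant has left the study, section 8.4.15 uses its own phrase and does not cite the 8.4.11 categories.
- *That 8.4.1 fixes the meaning of reasonable possibility for the tables.* Its explanation is limited to IND safety reporting. The firmer conflict is inside 8.4.11.
- *That the primary safety results are affected.* Those endpoints count unsolicited AEs, SAEs, AESIs and MAAEs whatever their relationship. Solicited ARs are related by definition, and the pause rules have their own attribution wording. Assessment is observer-blind, and one definition applies to every arm.
- *That an equally likely AE fits neither category.* The sentences under *Related* have no connective, so such an AE could be placed there on the lead test. The text is unclear, but it is not certain to leave a gap.

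**Conclusion.** Section 8.4.11 is internally inconsistent. If its comparative clauses are followed, investigator-assessed treatment-related counts of unsolicited AEs and SAEs will be at or below those under the reasonable-possibility standard that the section itself sets. The class of an equally likely AE is uncertain.

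A reader might conclude that treatment-related AEs are in fact under-counted, or put a percentage on it. Neither follows: the effect depends on which sentence investigators apply and on a share of events that the documents do not give. The consequence is confined to descriptive treatment-related summaries. This is a minor point, worth correcting because the correction is cheap.

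**What to change.** Reword 8.4.11 so that reasonable possibility alone decides the category:

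- In *Not related*, replace the comparative ground with wording such as: *another cause explains the AE so that there is not a reasonable possibility that the IP caused it*.
- In *Related*, delete the comparative sentence. Equally likely cases then fall under *Related*.

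Simply deleting both clauses would go too far. It would remove the only listed ground for *Not related* that rests on another cause, and leave a well-timed event with a clear alternative explanation to the lead sentence alone.

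Footnote the treatment-related tables to show which study parts were graded under the present wording. Related counts may rise slightly after the change and be less comparable across parts, for example between the 25 µg groups of Phase 2 NH and Phase 2 Extension if those parts are graded under different wording. The cost is protocol text, a note to sites and the footnote.

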8.4.12. Reporting Adverse Events

The Investigator is responsible for reporting all AEs that are observed or reported during the study regardless of their relationship to the IP or their clinical significance. If there is any doubt as to whether a clinical observation is an AE, the event should be reported.

All unsolicited AEs reported or observed during the study will be recorded in the AE section of the eCRF. Information to be collected includes type of event, time of onset, Investigator-specified assessment of severity (impact on activities of daily living) and relationship to the IP, time of resolution of the event, seriousness, any required treatment or evaluations, and outcome. The unsolicited AEs resulting from concurrent illnesses, reactions to concurrent illnesses, reactions to concurrent medications, or progression of disease states must also be reported. All AEs will be followed until they are resolved or stable or judged by the Investigator to be not clinically significant. The Medical Dictionary for Regulatory Activities (MedDRA) will be used to code all unsolicited AEs.

Any medical condition that is present at the time that the participant is screened but does not deteriorate should not be reported as an unsolicited AE. However, if it deteriorates at any time during the study, it should be recorded as an unsolicited AE.

